7.1.2. Analysis Methods for Albuterol Use

7.1.2.1. Pattern of Baseline Daily and Weekly Albuterol Use

A patient's pattern of baseline albuterol use is exhibited if, on any given day, during a given week, they do not take more than their average number of inhalations computed from day 1 to day 7.

Summary statistics including 95% CIs intervals of the proportion of patients exhibiting their individual weekly baseline albuterol use during each week of the 12 week study (Week 1, Week 2,..., Week 12) will be presented overall and by CE-COPD status and by CE-COPD severity (Yes: severe, moderate; No).

Summary statistics including 95% CIs intervals of the proportion of eMDPI time on study days when a patient did not take more than the average number of inhalations computed from day 1 to day 7 (number of days a given patient had no more than average baseline albuterol use) / total number of eMDPI study days for a given patient) will be summarized overall and by CE-COPD status and by CE-COPD severity (Yes: severe, moderate; No).

Week 1 and Week 2 and the first 14 day patient albuterol use patterns, "WK1:I#iD#dMTN#n," "WK2:I#iD#dMTN#n" and "D14:I#iD#dMTN#n" designation, will be summarized descriptively (counts and percent) overall and by CE-COPD status and by CE-COPD severity (Yes: severe, moderate; No).

7.1.2.2. Total Number of Inhalations in the Days Preceding the Peak of a CE-COPD

For patients who experienced a CE-COPD, summary descriptive statistics of the total number of inhalations taken in 1 day (eg, the 24-hour period on the day prior to the date of the CE-COPD symptom peak) and at 3, 5, 7, 10, 14, and 21 days preceding the date of the CE-COPD symptom peak, will be presented overall and by moderate CE-COPDs and severe CE-COPDs.

In this analysis, among patients experiencing more than 1 CE-COPD, the subsequent CE-COPDs can be considered a separate CE-COPD, distinct from the first (preceding) CE-COPD, provided the patient exhibited at least 1 day of baseline albuterol use after the first (preceding) CE-COPD's end date, as captured on the adverse event page, and prior to the subsequent CE-COPD's start date, as captured on the adverse event page. For patients who experience multiple CE-COPDs, all distinct CE-COPDs will be considered in this descriptive analysis. Descriptive summaries of the number of inhalations on the days prior to a CE-COPD will only be reported if the event does not overlap with a preceding CE-COPD. For example, if the date of symptom

peak for a patient's second CE-COPD occurs 12 days after the end date of the patient's first CE-COPD and there is at least 1 day of baseline albuterol use between these dates, then only the data collected on 1, 3, 5, 7, and 10 days (not 14 and 21 days) prior to the second CE-COPD will be included when computing the summaries measures.

Mean and 95% CIs of the total number of inhalations per day, for each eMDPI study day, will be summarized graphically. The number of patients contributing to the summary statistics at Day 7, 14, 21, 28, 35, 42, 49, 56, 63, 70, 77, and 84 will also be presented. Three lines graphs will be presented in 1 figure: "Overall" and by "CE-COPD Status" (Yes, No). Three line graphs will be presented in a second figure; "CE-COPD Status No", "CE-COPD Status Yes: Severe" and "CE-COPD Status Yes: Moderate".

A figure summarizing the mean (+/- minimum and maximum) of the total number of inhalations per day, for each patient experiencing multiple CE-COPDs, will be presented for the time period of 21 days prior to the date of symptom peak of the first CE-COPD to 21 days after the date of symptom peak of the last CE-COPD. The x-axis will be labeled -21, -20, ..., -1, 0, 1, 2, ...D, where day 0 is the date of symptom peak of the first CE-COPD and D is the study day number 21 days after the date of the symptom peak of the last CE-COPD.

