7.1.1. Albuterol Use Definition

Baseline albuterol use is defined as the mean number of inhalations per day from day 1 to day 7. If no inhalations were taken during study day 1 through study day 7, the ‘baseline inhalation’ is the first available inhalation after study day 7. For analyses relative to baseline albuterol use, patients who had a CE-COPD during study day 1 through study day 7 will be excluded.

Week 1 Patient Albuterol Use: Week 1 patient albuterol use is each patient’s total number of albuterol inhalations taken and the number of days used during the first week (study day 1 through study day 7) of study participation with an indicator of whether or not the most frequent daily usage of albuterol is in 1 of the following 3 categories: (a) 0 to 2 inhalations, (b) 3-6 inhalations and (c) > 6 inhalations. It is presented as WK1:I#iD#dMTN#n, where “i” is the number of albuterol inhalations and “d” is the number of days used in the first 7 days of the study, and “n” is an indicator of whether or not the most frequent daily usage of albuterol falls into one of the 3 categories. If there is a tie in the most frequent daily usage, the category with the highest number of inhalations will be reported. For example, “I28D7MTN2” indicates a total of 28 inhalations were taken, albuterol use was used each of the 7 days and the highest most frequent usage per day falls into category 2 with 3-6 inhalations.

Week 2 Patient Albuterol Use: Week 2 patient albuterol use is each patient’s total number of albuterol inhalations taken and the number of days used during the second week (study day 8 through study day 14) of study participation with an indicator of whether or not the most frequent daily usage of albuterol is in one of the following 3 categories: (a) 0 to 2 inhalations, (b) 3-6 inhalations and (c) > 6 inhalations. It is presented as “WK2:I#iD#dMTN#n”, where “i” is the number of albuterol inhalations and “d” is the number of days used in the second week of study, and “n” is an indicator of whether or not the most frequent daily usage of albuterol is in one of the 3 categories. If there is a tie in the most frequent daily usage, the category with the highest number of inhalations will be reported.

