7.2.2. Analysis Methods for Inhalational Flow Values

7.2.2.1. Actual and Change from Baseline in Study Day X Inhalational Flow Values Prior to the Peak of a CE-COPD

Among patients who experienced a CE-COPD, summary descriptive statistics of the actual inhalational flow values and change from baseline in daily inhalational flow values for MIF, inhalational volume, inhalation duration, and time to MIF at 1 day (eg, the 24-hour period on the day prior to the date of the CE-COPD symptom peak) and at 3, 5, 7, 10, 14, and 21 days preceding the peak of a CE-COPD, will be presented for all CE-COPDs and by moderate CE-COPDs and severe CE-COPDs.

In this analysis, among patients experiencing more than 1 CE-COPD, the subsequent CE-COPDs will be considered a separate CE-COPD distinct from the first (preceding) CE-COPD, provided the patient exhibited at least 1 day of baseline albuterol use after the first (preceding) CE-COPD’s date of symptom peak and prior to the subsequent CE-COPD’s date of symptom peak. For patients who experience multiple CE-COPDs (eg, 3), for a given number of days preceding a CE-COPD (eg, 7 days), if the (eg, third) CE-COPD overlaps with the time period of the preceding (eg, second) CE-COPD, the CE-COPD (eg, third CE-COPD) should not be included in the analysis.

Summary descriptive statistics of the actual inhalational flow values and change from baseline in daily inhalational flow values for MIF, inhalational volume, inhalation duration, and time to MIF will be presented for overall, by CE-COPD status, by CE-COPD severity (Yes: severe, moderate; No) and for the first occurrence of a single day increase of 20% from baseline use. For patients who experienced a CE-COPD, the single day increase of 20% from baseline use is the single day increase of 20% from baseline use prior to the exacerbation.

In addition, summary descriptive statistics of the maximum change from baseline in daily inhalational flow values for MIF, inhalational volume, inhalation duration, and time to MIF, will be presented overall and by CE-COPD status and by CE-COPD severity (Yes: severe, moderate; No). For patients who experienced a CE-COPD, the maximum change from baseline is the maximum change prior to the exacerbation.

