7.3.2. Analysis Methods for Total Daily Steps

7.3.2.1. Actual and Change from Baseline in Study Day X Total Daily Steps Prior to the Peak of a CE-COPD

Among patients in the ankle accelerometry cohort who experienced a CE-COPD, summary descriptive statistics of the actual TDS and change from baseline in TDS 1 day (eg, the 24-hour period on the day prior to the date of the CE-COPD symptom peak) and at 3, 5, 7, 10, 14, and 21 days preceding the peak of a CE-COPD, will be presented for all CE-COPDs and by moderate CE-COPDs and severe CE-COPDs.

In this analysis, among patients experiencing more than 1 CE-COPD, the subsequent CE-COPDs will be considered a separate CE-COPD distinct from the first (preceding) CE-COPD provided the patient exhibited at least 1 day of baseline albuterol use after the first (preceding) CE-COPD's date of symptom peak and prior to the subsequent CE-COPD's date of symptom peak. For patients who experience multiple CE-COPDs (eg, 3), for a given number of days preceding a CE-COPD (eg, 7 days), if the (eg, third) CE-COPD overlaps with the time period of the preceding (eg, second) CE-COPD, the CE-COPD (eg, third CE-COPD) will not be included in the analysis.

Among patients in the ankle accelerometry cohort, summary descriptive statistics of the actual TDS and change from baseline in TDS, will be presented for overall, by CE-COPD status, by CE-COPD severity (Yes: severe, moderate; No) and for the first occurrence of a single day increase of 20% from baseline use. For patients who experienced a CE-COPD, the single day increase of 20% from baseline use is defined as the single day increase of 20% from baseline use prior to the exacerbation.

In addition, summary descriptive statistics of the maximum change from baseline in TDS will be presented overall and by CE-COPD status and by CE-COPD severity. For patients who experienced a CE-COPD, the maximum change from baseline in TDS is the maximum change from baseline in TDS during the days prior to the exacerbation.

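### Repeat exacerbations enter the SAP's descriptive pre-peak summaries only after a day of baseline albuterol use, so they are selected on the predictor being summarised; the date windows conflict and the weekly baseline rule is ambiguous

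*SAP*

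**What the plan says.** SAP 7.1.1 sets the reference level: "Baseline albuterol use is defined as the mean number of inhalations per day from day 1 to day 7". SAP 7.1.2.1 then gives the test for the baseline pattern, which patients meet when "they do not take more than their average number of inhalations computed from day 1 to day 7". The time unit of that test is worded as "exhibited if, on any given day, during a given week", and the section does not say how many days of the week must pass. Two summaries follow. One is the "proportion of patients exhibiting their individual weekly baseline albuterol use during each week of the 12 week study". The other is a share of days for each patient, with numerator "number of days a given patient had no more than average baseline albuterol use" and the patient's eMDPI study days as denominator.

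SAP 7.1.2.2 uses the same idea to decide when a repeat CE-COPD is a separate event: "provided the patient exhibited at least 1 day of baseline albuterol use after the first (preceding") event. The window for that day varies:

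- **7.1.2.2, rule:** from the end date of the earlier event to the start date of the later one.
- **7.1.2.2, worked example:** from the end date of the earlier event to the symptom peak of the later one.
- **7.2.2.1 (inhalational flow):** from peak to peak, ending "and prior to the subsequent CE-COPD’s date of symptom peak".
- **7.3.2.1 (total daily steps):** from peak to peak, ending "and prior to the subsequent CE-COPD's date of symptom peak".
- **7.4.2.1 (sleep disruption):** no separation rule is stated.

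**The concern.** The pre-peak summaries exist to show what albuterol use, flow and steps look like before an exacerbation, and the study hypothesis is that albuterol use rises beforehand. A condition that admits a repeat event only after use has dropped to baseline for at least one day tends to keep the events preceded by lower use and to remove those preceded by persistently raised use. In 7.1.2.2 the selecting variable is the very quantity summarised. In 7.2.2.1 and 7.3.2.1 it is the study's main predictor.

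Because the windows differ, one patient's second event can appear in the flow and steps tables and be missing from the albuterol table, or the reverse, with no reason given.

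The weekly proportion in 7.1.2.1 has a separate problem. Its wording fits both a rule that one day suffices and a rule that every day must qualify. Two programmers could report very different percentages from the same data.

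**Working it through.** **Inputs.** From SAP 2.3: 360 evaluable patients, 1.05 and 1.14 events per year, 12 weeks, 91 expected events (73 to 110). From SAP 7.1.2.3: daily puffs are Poisson within a patient. From the example in SAP 7.1.1: 28 inhalations in 7 days, or 4 a day. The documents give neither the gap between events nor the level of use within it, so both are varied as assumptions.

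**1. The plan's event count.** The midpoint rate is (1.05 + 1.14)/2 = 1.095 a year. Events per patient are m = 1.095 × 12/52 = 0.2527, and 360 × 0.2527 = 91.0. The Poisson 2.5% and 97.5% quantiles are 73 and 110. This reproduces the plan's figures.

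**2. How many are repeats.** Expected repeats are 360 × [m − P(at least one event)].

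- Poisson: 360 × [0.2527 − (1 − e^−0.2527)] = 360 × (0.2527 − 0.2233) = 10.6.
- Negative binomial with shape 2 to 0.5 (assumed overdispersion): about 15 to 24.

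Repeats are thus about 12% to 27% of 91 events.

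**3. Chance that a repeat event is admitted.** Let S be the week 1 total, Poisson with mean 7λ, so the baseline mean is S/7. Use in the gap runs at r times λ. A day qualifies with probability F = P(Poisson(rλ) ≤ S/7). With g days in the gap, the chance of admission is the average over S of 1 − (1 − F)^g. For λ = 4:

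| Use in the gap | 3-day gap | 7-day gap |
|---|---|---|
| Baseline (r = 1) | 0.87 | 0.98 |
| 1.5 times | 0.52 | 0.78 |
| 2 times | 0.22 | 0.41 |
| 3 times | 0.02 | 0.04 |

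At doubled use over 7 days, admission is 0.68 for a baseline of 2 a day and 0.13 for 8 a day, so selection is stronger in heavier users.

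**4. Direction and possible size of the bias.** Suppose r is spread evenly from 1 to 3 with λ = 4 and a 7-day gap (an assumption). About 47% of repeat events are admitted. Mean use over the gap is 6.1 a day in those admitted and 9.6 in those dropped, against 8.0 in all.

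**5. The weekly rule.** In week 1 some day is always at or below that week's own mean, so the one-day reading gives 100% by arithmetic, while the every-day reading requires seven identical days. For a later week with unchanged Poisson use of 1 to 12 a day, the one-day reading gives 97.9% to 98.3% and the every-day reading 3.3% to 7.0%. The every-day figure depends on how variable daily use is:

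- 18% at 0.25 a day and 50% at 0.1 a day;
- 33% when 80% of a patient's days are identical, and 72% when 95% are;
- 4% to 26% in mixed cohorts averaging 2 to 6 a day.

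**6. The day-share measure in the same section.** It has no such ambiguity. At 4 a day the expected share of days at or below baseline is 54% when use is unchanged and 8% when it doubles.

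**The case against.** The best defence is clinical. A day back at baseline separates a new exacerbation from one that has not resolved, and without it, use still raised from the earlier event could be counted as a run-up to the next. That contamination is real but limited. Event start and end dates are already collected, 7.1.2.2 already cuts the look-back at the earlier end date, and 7.5.2.1 separates events by 14 CE-COPD-free days without using albuterol. Dates can do the job without selecting on the predictor.

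Three stronger readings are tempting and are not supported.

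- *The condition decides which repeat exacerbations count in the trial.* It is stated only for the descriptive pre-peak summaries. It does not enter the within-patient tests (7.5.2.1), the Kaplan-Meier analysis (7.5.2.2) or the proportion with recurrent events (7.5.2.4), and it is not stated for the t-test in 7.1.2.3. It also asks for at least one day, so the ambiguity of the weekly rule does not reach it.
- *On the every-day reading almost nobody qualifies.* That needs variable use of about 1 a day or more. The documents give no day-to-day variability, SAP 20.2 expects some patients with no use, and the inclusion criteria allow patients who had been on maintenance short-acting beta agonist.
- *The weekly baseline results are uninformative.* On the one-day reading at 4 a day, 98% of stable patients qualify against 41% of those who double their use. That discriminates, though weakly at low use (82% of those who double from 1 a day still qualify). The day-share measure carries the information without ambiguity.

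**Conclusion.** The concern holds for the descriptive pre-peak summaries in 7.1.2.2, 7.2.2.1 and 7.3.2.1. Repeat events are admitted according to albuterol use, which understates pre-peak use in those events, and the windows are inconsistent across sections. The probabilities of 0.98, 0.41 and 0.04 rest on independent Poisson days, a baseline of 4 a day, a 7-day gap and a constant rate within it. The direction of selection is the same at every baseline rate and gap length tried. The effect on overall tables is limited because repeats are about 11 of 91 events under Poisson, or 15 to 24 under the assumed overdispersion. No inferential result listed in 7.5.2.1 or 7.5.2.2 changes.

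The weekly proportion in 7.1.2.1 is a separate, smaller defect of wording. It is consequential for that table only, and a clear alternative is already planned beside it. Overall this is a worthwhile clarification, not a threat to the study's conclusions.

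**What to change.** - **Separation of events.** In 7.1.2.2, 7.2.2.1, 7.3.2.1 and 7.4.2.1, use one rule based on dates alone: a later CE-COPD is distinct if its start date is after the end date of the preceding one, with the look-back cut at that end date. Remove the albuterol-use condition and bring the worked example in 7.1.2.2 into line.
- **First events.** Because some use still raised from the earlier event may enter the look-back, also show each summary for first events only.
- **Weekly pattern.** In 7.1.2.1, define the week as at baseline when its mean daily inhalations do not exceed the baseline mean, and report it from week 2 only, since week 1 is 100% by construction. At 4 a day this gives about 53% when use is stable and 0.1% when it doubles; the doubled figure rises to about 2% at 2 a day and 7% to 8% at 1 a day. Alternatively, drop the weekly proportion and rely on the day-share measure.

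The cost is a few sentences in the SAP before database lock, simpler event programming and one extra set of descriptive tables. No new data are needed.

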2.3. Sample Size and Power Considerations

Assuming an expected dropout rate of 10%, it is recommended that 400 patients be enrolled so that 360 evaluable patients complete the study. These conclusions are based on a review of the relevant literature, as follows.

Based on previous studies of an exacerbation-prone COPD cohort ([Dransfield et al 2013](#), [Vogelmeier et al 2011](#), [Wedzicha et al 2013](#), [Wedzicha et al 2016](#)), it is expected that 91 (range, 73 to 110) CE-COPD events will occur over the 12-week evaluation period in this study based on reported CE-COPD exacerbation rates of 1.05 and 1.14 events per year. Furthermore, it is expected that 14% (14) of total exacerbations will be severe.

This sample size (ie, n=400 patients, 73 to 110 CE-COPD events) is considered adequate for the fulfillment of the study objectives to evaluate the relationship of albuterol use, inspiratory flow, SDI, and TDS data associated with a subsequent CE-COPD event. Per a previous study ([Jenkins et al 2013](#)), a statistically significant relationship was established between daily SABA usage and subsequent CE-COPD.

In the present study, approximately 73 to 110 CE-COPD events are desired because the model's fitting of the current study involves the analysis of multiple predictors as described in more detail below. Because the largest model considered has 7 covariates, it is desirable to have at least 70 events. The probability to observe at least 70 CE-COPD events is higher than 0.99.

Risk models published in the literature have typically included between 4 and 6 covariates/risk factors ([Bateman et al 2015](#), [Greenberg et al 2012](#), [Quezada et al 2016](#)) to examine the relationship between possible risk factors and a disease. When there is more than 1 covariate (risk factor) in the model, multiple logistic regression may be used to estimate the relationship of a specific covariate of interest (ie, albuterol use) to a primary outcome (ie, CE-COPD), adjusting for the other/remaining covariates (risk factors). In this case, the required sample size to estimate such a relationship is greater than that for univariate logistic regression.

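### SAP 7.1.2.1 tabulates early albuterol use as counts and percents of a combined code with hundreds of possible values, so the table by CE-COPD status will be mostly cells of 0 or 1 and will show little

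*SAP*

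**What the plan says.** SAP 7.1.1 defines a code for each patient for week 1, week 2 and days 1 to 14. On the first of these it says: "It is presented as WK1:I#iD#dMTN#n". The code has three parts:

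- i, the number of inhalations in the period, as an exact count;
- d, the number of days with use (0 to 7, or 0 to 14);
- n, the category into which daily use most often fell: 0-2, 3-6 or more than 6 inhalations, with ties going to the higher category.

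The SAP's own example is I28D7MTN2.

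SAP 7.1.2.1 then states that the code, called the "designation, will be summarized descriptively (counts and percent) overall and by CE-COPD status and by CE-COPD severity". Neither section groups i or d, and neither plans a separate summary of i, d or n for these periods. SAP 7 puts all endpoint analyses on the ITT set.

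**The concern.** Counts and percents suit a variable with few levels. Here the variable contains an ungrouped count, so two patients share a row only if they match exactly on total, days and category. Spread over enough codes, the CE-COPD and severe columns come close to a patient listing. A reader cannot then see whether patients who went on to exacerbate used more albuterol, used it on more days, or sat in a higher usual-use category at the start.

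The study sets out to explore the pattern and amount of albuterol use before a CE-COPD (SAP 1.1). A description of early use by status is a natural background to that, and for two of the three parts of the code this table is the only one planned. No test, model or decision depends on it, so what is at stake is the usefulness of one descriptive table.

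**Working it through.** **Size of the columns.** The inputs are from SAP 2.3: "it is recommended that 400 patients be enrolled so that 360 evaluable patients complete the study"; "based on reported CE-COPD exacerbation rates of 1.05 and 1.14 events per year"; "it is expected that 91 (range, 73 to 110) CE-COPD events will occur over the 12-week evaluation period".

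- Mean rate = (1.05 + 1.14)/2 = 1.095 per patient-year.
- Expected events = 360 × 1.095 × 12/52 = 90.97, which reproduces the plan's 91.
- The Poisson 2.5th and 97.5th percentiles are 73 and 110, which reproduces the range. P(at least 70) = 0.9901, in line with "The probability to observe at least 70 CE-COPD events is higher than 0.99".
- P(a patient has at least one event) = 1 − exp(−1.095 × 12/52) = 0.223, if events follow a Poisson process with the same rate in all patients. That is 0.223 × 400 ≈ 89 patients in the CE-COPD column (about 80 if N = 360).
- Severe events: 0.14 × 91 = 12.7. The plan says "it is expected that 14% (14) of total exacerbations will be severe". So the severe column rests on about 13 to 14 events.

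**Number of possible codes.** For a period of D days, let a, b and c be the days with 0-2, 3-6 and more than 6 inhalations (a + b + c = D). Let z of the a days have no use, and let M be the daily cap. Then d = D − z. The total i takes every whole number from (a − z) + 3b + 7c to 2(a − z) + 6b + Mc. The category n is the largest of a, b and c, ties to the higher. Counting the distinct (i, d, n):

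| Daily cap M | One week | 14 days |
|---|---|---|
| 8 | 328 | 1,246 |
| 12 | 512 | 1,972 |

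The cap of 12 is 2 inhalations × 6 four-hour intervals, used only to bound the count. Higher use would add codes.

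**Number of codes actually observed.** This needs a distribution of use, which the documents do not give. Assumptions: 400 patients; patient mean use follows a gamma distribution with mean 1 to 6 inhalations a day and shape 1 or 2; daily counts are Poisson; 22.3% have a CE-COPD; use is unrelated to status. Cells are counted over codes held by at least one patient. The table gives averages over 200 simulated data sets, with ranges across the two shapes.

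| Mean/day | Week 1: distinct codes | CE-COPD cells of 0 or 1 | No-CE-COPD cells of 0 or 1 | 14-day: distinct codes | CE-COPD cells of 0 or 1 |
|---|---|---|---|---|---|
| 1 | 70-77 | 72-78% | 38-45% | 133-138 | 86-88% |
| 2 | 106-111 | 80-83% | 40-47% | 190-196 | 93% |
| 3 | 129-134 | 85-86% | 45-50% | 217-219 | 94-95% |
| 4 | 144-150 | 87-88% | 48-52% | 231-234 | 95% |
| 6 | 163-174 | 90-91% | 52-56% | 240-256 | 96-97% |

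Rounded, that is about 70 to 175 week 1 codes and 135 to 255 14-day codes. In the severe column 98-100% of cells hold 0 or 1.

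A direct check: 89 CE-COPD patients over 70 to 175 codes is 89/70 = 1.3 down to 89/175 = 0.5 patients per code. For 14 days it is 89/135 = 0.7 down to 89/255 = 0.3.

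**Wider assumptions.** Mean use of 1 to 8 a day, extra day-to-day variation, use in pairs of puffs and up to 10% never-users give 44 to 235 week codes (11-59% of 400) and 78 to 311 14-day codes (20-78%). In the scenarios split by status (2 to 8 a day), on average 0 to 3 codes have an expected CE-COPD count of at least 5. At 4 to 8 a day this is usually none or one, the no-use code.

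**What else the SAP shows by status.**

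- 7.1.2.2 plots mean inhalations with 95% CIs for each study day. This covers the average amount in days 1 to 14, but not days used, usual-use category or the spread between patients.
- 7.1.2.1 compares each patient's use with that patient's own day 1-7 mean, so it does not show how much was used.
- 7.1.2.5 (maximum in 24 hours) and 10.2 (days with use; average and maximum exposure) are not confined to the first two weeks.
- 5.3 does not list albuterol use among the baseline characteristics.

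**The case against.** The strongest reply is that this is one display among several. The objective concerns use before an exacerbation, and that is served by the counts at 1 to 21 days before the peak (7.1.2.2), the test of 7 days against the prior 7 (7.1.2.3), the days-to-increase summaries (7.1.2.4) and the paired-week comparisons (7.5.2.1). None of these uses the code. Early amount by status can be read from the plot in 7.1.2.2, and the three parts can be recovered from any patient's code. All of this stands, and it keeps the point small.

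A reader might also infer more than the documents support:

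- **That there are nearly as many codes as patients.** Under the main assumptions the observed codes are about 17-44% of N for a week and 34-64% for 14 days. Only about 5-20% of patients would hold a unique week 1 code.
- **That almost every cell is 0 or 1.** This is close to true for the CE-COPD and severe columns. In the week 1 column without CE-COPD it is 38-56%.
- **That the table can show no pattern.** The no-use code, and at low mean use a few low-use codes, can be large enough to compare.
- **That early use is compared by status only here.** The daily plot contradicts this.

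What remains is that days used, usual-use category and the patient-level distribution of early totals have no other summary by status.

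**Conclusion.** The point holds as a matter of table design. The code has hundreds of possible values for about 400 patients. Under assumed mean use of 1 to 6 inhalations a day, about 70-91% (week 1) and 86-97% (14 days) of cells in the CE-COPD column would hold 0 or 1 patient, with the severe column sparser still. The table would show little beyond the no-use code and a few low-use codes.

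The count of possible codes follows from the SAP's definitions and the chosen daily cap. The observed counts and cell percentages depend on a use distribution that is assumed, and lower use or use in pairs of puffs would reduce them. The consequence is minor: a descriptive table in an exploratory study, with no effect on any test or model.

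**What to change.** In SAP 7.1.2.1, replace the tabulation of the code. For week 1, week 2 and days 1 to 14, overall and by CE-COPD status and severity, summarise:

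- total inhalations: n, mean, SD, median, minimum, maximum;
- number of days used: the same statistics;
- usual-use category: n (%).

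These are the statistics that SAP 4.1 already sets for continuous and categorical variables. Keep the combined code in the patient listing.

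The gain can be sized roughly. In scenarios with mean use of 2 to 8 a day and use assumed 1.5 times higher in patients with CE-COPD, the smallest of the three categories holds on average about 8 to 18 CE-COPD patients, whereas 70-95% of codes hold only 1 or 2 patients from the whole cohort.

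The cost is one SAP sentence and a shorter table. No new data are needed and nothing is lost.
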